5.2.1.3 Adverse Event Follow-Up

Record all reportable serious and non-serious AEs on the appropriate eCRF including the onset, duration, severity, relationship to the study drug, and ultimate management. All AEs reported during the treatment phase should be recorded and followed until the AE has subsided, or stabilized or until the end of the study, whichever occurs first. The study will be stopped at any time if new knowledge is gained and the risk-benefit ratio is no longer favorable for the participating patients

5.2.2 Other Safety Monitoring

5.2.2.1 Laboratory Evaluations

Optional biomarker with buccal, urine and stool samples will be collected for the biomarker analysis. At day 0/1, day 15, day 30 and day 60. The samples will be kept in a laboratory at Rochester campus. These samples may be used to assess (but not limited to) markers of inflammation and senescence.

5.3 Withdrawal of Patients from the Study

Patients have the right to withdraw from the study at any time during the course of the study. However, every effort should be made, within the bounds of safety, patient choice and the provisions of informed consent, to have each patient complete the study up to and including the last protocol-specified study visit. If the study medication jeopardizes the patient's health or if the patient wishes to discontinue for any reason, study medication can be discontinued but the patient should be encouraged to remain in the study for the follow-up visit up to the End of Study visit. If the patient does not wish to pursue the protocol follow-up visit, the option for a last contact at the end of the study to obtain their vital status should be proposed. Patients who are not compliant during the active treatment period should be counseled on the importance of complying with study requirements and be allowed to remain in the study. No patient who has withdrawn their consent from the study during the active treatment period should be replaced.

In the case of an adverse event or safety concern, the study medication may be withheld temporarily, or the dose reduced, as per investigator judgment.

Patients withdrawn at any time from the study during the active treatment period should complete all last protocol-specified visit requirements (End of Study Visit, the reason for withdrawal from the study, the date of the last visit and the date of the last dose of double-blind medication will be clearly documented in the eCRF).

5.4 Study Completion

The study will end when the last randomized patient will have completed his (or her) 60 day follow-up phone contact. Completion of the study by a patient should be clearly indicated in the eCRF, along with the date of the last visit and the date of the last dose of double-blind medication.

Patients will be remunerated for participation in the study; they will receive \$25 after completing Day 15, Day 30 and Day 60.

6 STUDY MEDICATION

Mayo Research pharmacy will prepare and dispense study medication (fisetin and placebo) with appropriate labeling to include a statement that these products are for investigational use only.

6.1 Medication Dispensing

Study medication may be dispensed by the designated pharmacist or a qualified investigative site representative, according to a detailed set of dispensing instructions. Study medication may also be shipped directly to the patient's home depending on evolving circumstances related to COVID-19.

6.2 Dosage Regimen

At randomization, patients will be dispensed Fisetin capsules or placebo to match Fisetin capsules. Patients will be instructed to take 20mg/kg on days 0 and 1 and another 20mg/kg on days 8 and 9 according to the detailed set of dispensing instructions outlined on the label.

7 DATA COLLECTION

Electronic Case Report Forms (eCRF) for all patients will be supplied. These are to be completed as instructed. Original source documents and other study documentation will be maintained at the study site. Risk-based monitoring will be performed by the study team.

8 DATA ANALYSIS AND STATISTICAL CONSIDERATIONS

8.1 Statistical Power and Sample Size Considerations

All main analyses in COVFIS-HOME will be conducted on an intention-to-treat basis. Assuming 75 subjects/ group with a significance level of 0.05, the study will have 80% power to detect an odds ratio of 2.24 comparing the placebo- to Fisetin-treated group, using the 7-point severity score at Day 30 as the endpoint in an ordinal logistic regression model.

Analysis population

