OUTCOMES: The primary endpoint will be the rate of complications related to COVID-19 (CoV) disease using a 7 point score adapted from the WHO Ordinal Scale for Clinical Improvement of CoV (Appendix A) in the 30 days following randomization. The secondary endpoint is to determine safety and tolerability of treatment with Fisetin in this patient population. Exploratory objectives are to evaluate links between soluble and genetic markers of senescent cell abundance, SASP factors, inflammation, viral load, and treatment effects and if Fisetin treatment during acute CoV infection decreases Long-hauler syndrome at Days 60.

STATISTICAL RATIONALE AND ANALYSIS: All main analyses in COVFIS-HOME will be conducted on an intention-to-treat basis. Assuming 75 subjects/ group with a significance level of 0.05, the study will have 80% power to detect an odds ratio of 2.24 comparing the placebo- to Fisetintreated group, using the 7-point severity score at Day 30 as the endpoint in an ordinal logistic regression model.

A fully independent 5-member Data and Safety Monitoring Board (DSMB) will be established and will review unblinded safety data as detailed in the DSMB charter. An interim analysis is planned after approximately 50% of randomized patients have completed 30 days of follow-up.

The DSMB charter will pre-specify the methods of interim efficacy analyses and the rules for early study termination, approved by all board members. The stopping rules for efficacy will be based on the O'Brien-Fleming α -spending function or on a similar conservative approach so that the impact on the final alpha level will be negligible. Futility will be assessed by computing conditional power. The DSMB will have the option of recommending early study termination because of overwhelming efficacy, early termination for futility, or continuation of the trial as planned.

The primary analysis of efficacy will be based on the intent-to-treat principle. The primary endpoint will be compared between the two treatment groups using a chi-square test. Secondary endpoints will be analyzed similarly.

ANTICIPATED TOTAL NUMBER OF RANDOMIZED PATIENTS: Approximately 150 patients in total will be randomized in this study.

STUDY LOCATION: Mayo Clinic Minnesota.

GLOSSARY

AE Adverse Event/Adverse Experience

AFFIRM Alleviation by Fisetin of Frailty, Inflammation, and Related Measures Trial

ALT Alanine Aminotransferase

ARDS Acute Respiratory Distress Syndrome

AST Aspartate Aminotransferase

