Longhauler Syndrome: Initial reports from WHO-China in February described clinical recovery from time of onset of COVID symptoms to be between 2-6 weeks, the latter being patients with more severe cases (https://www.who.int/docs/default-source/coronaviruse/situation-reports/20200306-sitrep-46-covid-19.pdf?sfvrsn=96b04adf 4). As more information becomes available, patients are coming forward with experiences of longer recovery times and lingering symptoms, Long Covid, Long-haul Covid, or Long-haulers¹⁰⁻¹². Though largely undefined, "Long-haulers" denotes patients who experience persistent symptoms after having acute COVID-19. While the full impact of long COVID is widely unknown, some sources are reporting upwards of 10% of patients experiencing symptoms lasting greater than 3 weeks¹². An earlier study done in Italy showed that 87% of hospitalized patients reported at least one ongoing symptom 60 days after onset of first COVID-19 symptoms, with 55% of patients reporting 3 or more ongoing symptoms¹³. These long lasting symptoms can occur in adults across all age groups, regardless of pre-existing conditions¹⁴. The long term sequelae of the virus are largely unknown, but early reports of significant lung damage^{15,16} and persistent myocardial inflammation¹⁷ are concerning, making the discovery of long term impact at the mechanistic level all the more urgent.

Cellular Senescence: Cellular senescence contributes to age-related dysfunction and multiple diseases throughout the lifespan. Senescent cell burden is very low in young individuals but increases with aging in several tissues. These include adipose tissue, skeletal muscle, heart, kidney, brain, bone, and skin^{5,18-24}. Senescent cells accumulate at sites of pathology in multiple chronic diseases, including, among others, the lungs in chronic obstructive pulmonary disease, asthma, idiopathic pulmonary fibrosis (IPF), and smoking, adipose and other tissues in diabetes/ obesity, the brain in Alzheimer's and other dementias, and blood vessels and the heart in cardiovascular disease.

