2 STUDY OBJECTIVES

The primary objective of this study is to determine whether short-term treatment with Fisetin reduces

the rate of complications related to COVID-19 (CoV) disease using a 7 point score adapted from the WHO Ordinal Scale for Clinical Improvement of CoV (Appendix A). The secondary objective is to determine safety and tolerability of treatment with Fisetin in this patient population. Exploratory objectives are to evaluate links between soluble and genetic markers of senescent cell abundance, SASP factors, inflammation, viral load, and treatment effects.

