3.3 Screening Evaluations and Randomization

Screening evaluations will include a review of the patient's medical history and assessment of concomitant medications to determine if the patient qualifies for the study. Patients who meet all inclusion criteria and no exclusion criteria will be randomized to receive the study drug or placebo. All patients must be randomized within 10 days of the diagnosis of COVID-19 infection.

Women of childbearing potential must have a negative urine pregnancy test result after the time of randomization, but before IP administration in order to qualify. Qualifying patients will be randomized to receive placebo or fisetin administered in a blinded manner. Blinded randomization will be performed through an automated Interactive Web Response System (IWRS). 75 patients will be randomized to active treatment and 75 patients will be randomized to placebo for a total of 150 randomized patients.

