Appendix A Detailed Study Safety Parameters

1. Demographics and Medical/Surgical History

The following elements of demographics, medical/surgical history will be recorded at the Screening Visit:

- age
- ethnic origin
- sex
- smoking history
- history of diabetes
- history of hypertension
- history of dyslipidemia
- prior cardiac events/heart failure
- prior obstructive pulmonary disease
- prior other respiratory disease

2. Physical Appearance

- 1. weight
- 2. height
- 3. BMI \geq 30 kg/m²

4. Detailed Visit Summary

Screening Visit (Days -2 to 0)

Patients will be pre-screened and inclusion and exclusion criteria will be reviewed prior to being recruited for the study.

- Screening Labs (within 6 months prior to randomization): CBC with diff and comprehensive metabolic panel with assessment of liver and kidney function tests
- Pregnancy test (women of childbearing potential)

Subjects who qualify should be immediately randomized. Randomization and dosing should occur on the same day if possible.

Baseline (Day 0 & Day 1) – IP Administration

- Mail in kit for buccal swab, urine and stool sample prior to first dose of IP administration, if applicable
- SF 36 Health Survey
- Determination of Ordinal Scale Score.
- The 1st IP administration will occur on Day 0.
- The 2nd IP administration will occur on Day 1 (12 -36 hours after the 1st IP administration).
- Day 8 & Day 9 IP Administration Phone call visit with the study team as a reminder for IP administration. This call can occur within a 2 day window (+ or -) of day 8; study drug administration will still occur on day 8 and day 9.
- Determination of Ordinal Scale score.
- Review of adverse events.
- SF-36 Health Survey

- The 3rd IP administration will occur on Day 8.
- The 4th IP administration will occur on Day 9 (12- 36 hours after the 3rd IP administration).

Day $15 - (\pm 2 \text{ days})$

- Determination of Ordinal Scale score.
- Review of adverse events.
- SF-36 Health Survey
- Mail in kit for buccal swab, urine and stool sample, if feasible

Day 30 (-2 to +7 days)

- Determination of Ordinal Scale score.
- Review of adverse events.
- SF-36 Health Survey
- Mail in kit for buccal swab, urine and stool sample, if feasible

Day 60 (±14 days)

- Determination of Ordinal Scale score.
- Review of adverse events.
- SF-36 Health Survey
- Mail in kit for buccal swab, urine and stool sample, if feasible

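### Does the 80% power claim at odds ratio 2.24 fail because no category spread or missing-score rate is stated?

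*Combined protocol and SAP*

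**What the plan says.** Section 8.1 states that with 75 subjects per group and a significance level of 0.05, "the study will have 80% power to detect an odds ratio of 2.24 comparing the placebo- to Fisetin-treated group". The synopsis, under Statistical Rationale and Analysis, repeats this and, like Section 8.1, ties it to a model "using the 7-point severity score at Day 30 as the endpoint in an ordinal logistic regression model". Section 8.2.1 makes the tests two-sided. Section 8.2.3 says the sample size was computed at 0.05 without the small interim adjustment.

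The 75 per group is the number randomized, not the number expected to have a score. Section 3.3 reads "75 patients will be randomized to active treatment and 75 patients will be randomized to placebo for a total of 150 randomized patients". Section 5.3 does not replace patients who withdraw consent during treatment. Section 8.1.2 keeps every randomized patient in the intention-to-treat population.

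Neither the synopsis nor Section 8 gives an expected distribution over the seven levels, a missing-score rate or a rule for a missing Day 30 score. The nearest clinical information is in the long-hauler paragraph of Section 1.1. Early reports "described clinical recovery from time of onset of COVID symptoms to be between 2-6 weeks"; "some sources are reporting upwards of 10% of patients experiencing symptoms lasting greater than 3 weeks"; and "87% of hospitalized patients reported at least one ongoing symptom 60 days after onset of first COVID-19 symptoms". None of these is on the 7-point score.

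**The concern.** An odds ratio, a sample size and an alpha level do not fix the power of a proportional-odds test. The spread of patients over the categories matters too. If nearly everyone sits on one level, most pairs of patients are tied and carry no information about treatment. A missing score removes a patient from the comparison altogether.

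Patients enter this trial as outpatients (Section 4.2.1), and many could have recovered by Day 30, so clustering on the best level is conceivable. The 80% is the only figure offered for the choice of 150. If it depended on an even spread that the trial is unlikely to see, the trial could be much weaker than it appears, and a null result would be hard to interpret.

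**Working it through.** **Inputs.** N = 150 in total, 1:1 allocation, odds ratio 2.24 (Sections 3 and 8.1); two-sided 0.05 (Section 8.2.1). The spread over levels and the missing-score rate are not stated, so they are varied below as assumptions.

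**Formula.** For a proportional-odds comparison with 1:1 allocation:

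power = Φ( ln(OR) × √(N × V / 12) − 1.960 ), with V = 1 − Σp³,

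where p are the category shares averaged over the two arms. Here ln(2.24) = 0.8065.

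**Step 1: reproduce the stated figure.** Seven equal levels: V = 1 − 7 × (1/7)³ = 0.980. Then 0.8065 × √(150 × 0.980 / 12) = 2.822, less 1.960 = 0.862, and Φ(0.862) = 80.6%. The stated 80% is confirmed. A simulation with seven equal levels in the placebo arm, 75 per arm and a tie-corrected Wilcoxon test gives 79.8%.

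**Step 2: how close is this to the limit?** Even if V reached 1, power would be 81.4%. By number of equally filled levels:

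| Equal levels | V | Power at N = 150 | N for 80% power |
|---|---|---|---|
| 7 | 0.980 | 80.6% | 147.8 |
| 6 | 0.972 | 80.3% | 149.0 |
| 5 | 0.960 | 79.8% | 150.8 |
| 4 | 0.938 | 78.8% | 154.5 |
| 3 | 0.889 | 76.7% | 162.9 |
| 2 | 0.750 | 69.5% | 193.1 |

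The stated figure is therefore near the top of what the design can deliver.

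**Step 3: moderate departures (assumed).**

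- Pooled split 30/30/20/10/5/3/2%: V = 0.937, power 78.8%.
- One level holding 42% of patients, the other six equal: V = 0.920, power 78.1%.
- Seven equal levels with 5% missing (N = 142.5): 78.5%. With 10% missing (N = 135): 76.3%. With 20% missing (N = 120): 71.4%.

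On the odds-ratio scale, the effect with 80% power is exp(2.802 / √(N × V / 12)). With seven equal levels it is 2.23 with complete scores, 2.27 with 5% missing and 2.33 with 10% missing.

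**Step 4: strong clustering (assumed; no such distribution is in the documents).** The share is that of placebo patients on the best level, with the other six equal and the Fisetin arm shifted by odds ratio 2.24. N = 150.

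| Placebo share on best level | Formula | Simulation |
|---|---|---|
| 50% | 71.5% | 70.7% |
| 60% | 65.0% | 63.9% |
| 70% | 55.7% | 53.8% |
| 80% | 42.5% | 40.5% |
| 90% | 25.2% | 22.8% |

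**Step 5: do the documents place the trial in Step 3 or Step 4?** They do not. The Section 1.1 figures point both ways: recovery within weeks for many, yet a large majority of one hospitalized series still symptomatic at 60 days. Outpatient entry alone does not fix the Day 30 distribution. Nor do the documents give a loss rate. Several provisions limit loss: Day 30 is a phone contact with a window of −2 to +7 days (Table 1, Timetable of Visits), patients who stop study drug are encouraged to stay in follow-up (Section 5.3), and payment is tied to completing Days 15, 30 and 60 (Section 5.4).

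**The case for a change.** The strongest case for a change is that a near-maximum is presented as a plain property of the design. Uneven spread and lost scores can only pull it down. The reader has no means of telling whether planned power is close to 80% or far below it, although this is the sole justification for 150 patients. Intention-to-treat says who is analysed but not what score a patient without a Day 30 contact receives, and the fallback contact in Section 5.3 secures vital status only. The trial also plans a conditional-power futility look (Section 8.2.3). A sentence and a small table would settle the matter at almost no cost.

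Much of this is right as description. The inputs are absent, 80% is near the ceiling, and heavy clustering would be costly. It falls short in three ways. First, 80% is not a cliff edge: a far from even split, or 5% missing, leaves power within about two points of the claim, which is small for a pilot. Second, every figure below about 69% at N = 150 in the clustering table comes from an assumed placebo share of 60% or more; the documents show an unstated input, not low power. Third, stating the input would leave the 150 patients, the model and the results as they are. At the interim the pooled spread would be observed, so conditional power need not rest on a planning guess.

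The scale levels do not appear in Appendix A as it can be read here, although Section 2 refers to that appendix for the score. That may be a loss in text extraction and carries no weight.

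**Conclusion.** The power statement is arithmetically sound and needs no correction. It is a near-best case: 80.6% by formula with seven equal levels and complete scores, against a theoretical limit of 81.4%. Moderate unevenness or 5% missing scores lowers it by about 1 to 2 points from the stated 80%, and 10% missing gives 76.3%. The drop to about 71% or 41% arises only if 50% or 80% of placebo patients share the best level, which is an assumption with no support either way in the documents.

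What is missing is detail behind a planning figure. A statistician can supply it with the formula above, and supplying it changes neither the sample size, nor the conduct, nor the analysis. All figures apply to the ordinal model at two-sided 0.05. Section 5.1 defines the primary endpoint as death or hospitalization and Section 8.2.1 tests it by chi-square. That conflict with the ordinal model is a separate matter and the more important one: until it is reconciled, it is not settled that the ordinal power figure describes the primary analysis, and refining the figure alone would gain nothing.

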5 STUDY METHODOLOGY

5.1 Efficacy Outcomes

The primary endpoint will be the composite of death or the need for hospitalization due to COVID-19 infection in the first 30 days after randomization. The secondary endpoints will consist of the components of the composite primary endpoint; and the need for mechanical ventilation in the first 30 days after randomization. Exploratory endpoints will include associations between senescent biomarkers and long hauler syndrome effects.

Biomarkers endpoints:

Samples received from participants will be kept frozen until evaluation of biomarkers. Samples will be stored and processed at Mayo Clinic Rochester.

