8.2 Data analysis

8.2.1 Analysis of efficacy outcomes

The primary analysis of efficacy will be based on the intent-to-treat principle. The primary endpoint will be compared between the two treatment groups using a chi-square test. Logistic regression models might also be used to compare the primary endpoint between the two treatment groups while accounting for important baseline characteristics. Secondary endpoints will be analyzed similarly. Exploratory analysis (biomarkers) will include logistic regression models with the primary/secondary endpoints as dependent variables and with treatment group, biomarker and treatment group x biomarker interaction as independent variables.

All statistical tests will be two-sided and conducted at the 0.05 significance level, with the exception of the primary analysis that will be conducted at a slightly lower level to account for the interim analysis. Statistical analyses will be done using SAS version 9.4 or higher.

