8.2.3 Interim analysis

A fully independent 5-member Data and Safety Monitoring Board (DSMB) will be established and will review unblinded safety data as detailed in the DSMB charter. An interim analysis is planned after approximately 50% of randomized patients have completed 30 days of follow-up. The DSMB charter will pre-specify the methods of interim efficacy analyses and the rules for early study termination, approved by all board members. The stopping rules for efficacy will be based on the O'Brien-Fleming alpha-spending function or on a similar conservative approach so that the impact on the final alpha level will be negligible. Futility will be assessed by computing conditional power. The DSMB will have the option of recommending early study termination because of overwhelming efficacy, early termination for futility, or continuation of the trial as planned.

The final analysis of the primary endpoint will be conducted at a significance level slightly below

the 0.05 level to account for the interim analysis. However, since this will have a negligible impact on power, the sample size calculation was calculated using a significance level of 0.05.

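### The 80% power is for the 7-point score at Day 30, but the primary endpoint covers the whole 30 days and is tested by chi-square, so the figure does not belong to the stated endpoint

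*Combined protocol and SAP*

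**What the plan says.** **Power.** Section 8.1, repeated in the synopsis under Statistical Rationale and Analysis, reads "Assuming 75 subjects/ group with a significance level of 0.05", "the study will have 80% power to detect an odds ratio of 2.24", "using the 7-point severity score at Day 30 as the endpoint in an ordinal logistic regression model". This is a status at one time point.

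**Primary endpoint.** The synopsis (Outcomes) gives the rate of COVID-19 complications on the 7-point score "in the 30 days following randomization". Section 5.1 gives a binary composite of death or COVID-19 hospitalization "in the first 30 days after randomization". The population paragraph in Section 1.1 (Background) also names hospitalization and death. All but the last, which sets no period for the outcome itself, run over 30 days.

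**Test.** The synopsis and Section 8.2.1 name a chi-square test, with logistic regression as a possible adjusted analysis. Neither mentions a Day 30 score.

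**Data collection.** Table 1 in Section 3.4 records the ordinal score at Days 0, 8, 15, 30 and 60. Appendix A heads the relevant contact "Day 30 (-2 to +7 days", that is, Days 28 to 37. Appendix B, Section 3.6, has study endpoints entered in the eCRF within 24 hours of awareness. Appendix A is cited as the source of the scale but lists only when it is scored, not its categories.

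**The concern.** A score taken on one day and a record of what happened over 30 days are different variables. A patient admitted on Day 5 and home by Day 12 is an event under Section 5.1. A Day 30 status score does not register that admission. The same holds for ventilation, or for oxygen use if the scale grades it.

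No passage says whether the Day 30 score, the worst score or any event is analysed, and no rule combines the scheduled scores. Two things are at stake. The first is whether the primary analysis sees the events that the trial aims to reduce. The second is whether the stated power describes that analysis. While the choice is open, it could also be made after data have been seen.

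**Working it through.** **Inputs.** From Section 8.1: 75 per arm (N = 150), alpha 0.05, OR 2.24, 80% power. Section 8.2.1: "All statistical tests will be two-sided and conducted at the 0.05 significance level". Section 8.2.3 confirms that "the sample size calculation was calculated using a significance level of 0.05", with no reduction for the interim look. The documents give no category proportions, event rate or dropout, so every distribution below is an assumption.

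**Step 1: the plan's own figure.** The Whitehead proportional-odds formula for 1:1 allocation is

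N = 12(z_α/2 + z_β)² / [ln(OR)² × K], with K = 1 − Σp̄³,

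where p̄ are the category proportions averaged over the arms. Equivalently, power = Φ(ln(OR) × √(N × K/12) − 1.960). Here ln(2.24) = 0.8065.

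With seven equal categories, K = 1 − 7 × (1/7)³ = 0.9796. Power = Φ(0.8065 × √(150 × 0.9796/12) − 1.960) = Φ(2.822 − 1.960) = 80.6%, and 80% needs N = 147.8. The figure is reproduced.

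**Step 2: sensitivity to spread.** Eighty per cent at N = 150 needs K = 0.965. Moderate unevenness does little harm: a pooled split of 25/20/20/15/10/5/5 gives K = 0.964 and power 79.9%, and 30/20/20/10/10/5/5 gives 79.6%. Concentration in one category does the damage.

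Example with 60% of placebo patients in the lowest (best) category and the rest spread evenly:
- fisetin odds of the lowest category = 1.5 × 2.24 = 3.36, a share of 77.1%;
- pooled share = 68.5%;
- K = 1 − 0.3219 − 0.0009 = 0.677;
- power = Φ(2.347 − 1.960) = 65%.

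| Placebo share in lowest category (assumed) | K | Power at N = 150 | Total N for 80% |
|---|---|---|---|
| 40% | 0.872 | 76% | about 166 |
| 60% | 0.677 | 65% | about 214 |
| 80% | 0.386 | 43% | about 375 |
| 90% | 0.205 | 25% | about 706 |
| 98% | 0.043 | 9% | about 3,375 |

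A steep rather than even spread over the other six categories changes power by 0.002 or less for shares of 60% to 98%.

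**Step 3: the Section 5.1 composite.** Take OR 2.24 as placebo odds over fisetin odds of an event, with n = 75 per arm:

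power = Φ{[d√n − 1.960 × √(2p̄(1 − p̄))] / √(p_c(1 − p_c) + p_t(1 − p_t))}, with d = p_c − p_t.

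At p_c = 10%, the fisetin odds are 0.1111/2.24 = 0.0496, so p_t = 4.73% and d = 0.0527. Power = Φ[(0.4567 − 1.960 × 0.3693)/0.3675] = Φ(−0.727) = 23%.

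| Placebo event rate (assumed) | Fisetin rate | Power | n per arm for 80% |
|---|---|---|---|
| 5% | 2.3% | 14% | 754 |
| 10% | 4.7% | 23% | 384 |
| 20% | 10.0% | 40% | 201 |
| 30% | 16.1% | 53% | 143 |
| 50% | 30.9% | 67% | 103 |

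**Step 4: what a Day 30 snapshot could miss.** At an assumed 10% cumulative rate, 75 × 0.10 = 7.5 placebo patients have an event. If 50%, 80% or 90% of them are discharged alive before Day 30, then 3.75, 1.5 or 0.75 are still in hospital or dead on that day.

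**The case against.** A reader might infer that a patient discharged before Day 30 is scored as having no complication, so that the analysis discards most events. The documents do not support this as fact. Day 30 timing appears only in the power sentence. Under Section 5.1 the same patient is an event, and Appendix B provides for recording it. The scale categories are not listed, so nobody can say where a discharged patient scores. The Background cites a study in which 87% of hospitalized patients still had a symptom 60 days after onset. If any category reflects symptoms, such patients may not be at the bottom of the scale.

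A reader might also infer that the Day 8 and Day 15 scores go unused. No passage says so, and the synopsis wording is compatible with using them. Nor does the 30-day period come from the objective: Section 2 sets no time frame, and the synopsis objective speaks of death and long-term complications. The period belongs to the endpoint.

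Finally, one cannot say outright that 80% power is not reached on the Day 30 score. That depends on an unknown distribution, and Step 2 shows that moderate unevenness is harmless.

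All of this stands, and it limits the claim. It does not remove the mismatch: the objection protects the events only by reading the endpoint as the composite, and the composite is not what Section 8.1 powers.

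**Conclusion.** The inconsistency is real and should be settled before any unblinded efficacy analysis. The stated power belongs to a Day 30 ordinal score. The stated endpoint covers 30 days, appears in two forms (ordinal and binary), and is tested by chi-square.

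Loss of transient events is conditional: it occurs if the Day 30 score is analysed, as the power statement assumes. If the composite is analysed instead, COVID-19 hospitalizations are kept, but power at OR 2.24 is 14% to 67% for assumed placebo rates of 5% to 50%.

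On the ordinal reading, 80% holds for equal or moderately uneven categories and drops to 65% to 9% as the placebo share in the lowest category rises from 60% to 98%. Eligible patients are outpatients not under immediate consideration for hospitalization, so near-even filling of all seven levels on Day 30 looks unlikely, but the documents give no figure either way. What is certain is that the 80% is unsupported for the endpoint as defined.

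**What to change.** Name one primary variable that covers the whole 30 days. Either option is coherent:

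- **Worst post-randomization score through Day 30**, built from the Day 8, 15 and 30 scores plus dated admissions, ventilation and deaths between contacts. Leave out the Day 0 score, or the variable cannot register improvement from baseline. Analyse it with a proportional-odds model.
- **The Section 5.1 composite**, analysed by chi-square or logistic regression.

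Then:

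1. Make the synopsis and Sections 1.1 (Background), 5.1, 8.1 and 8.2.1 agree on the endpoint and the test.
2. Fix ascertainment at calendar Day 30 whatever the call date. A Day 28 call is completed from the Day 60 contact, and a Day 37 call does not bring in events after Day 30.
3. List the seven categories in Appendix A.
4. Restate the power with the assumed distribution or event rate shown.

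The cost is protocol and SAP wording, a derived variable, and event dates on the eCRF where they are not already collected. The contacts and endpoint reporting are already planned. The downside is a less favourable power statement: choosing the worst score keeps the target events but does not by itself restore 80%.
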